### 7.2 Statistical Methods

Student's t-test to compare MEMRI and DEMRI measurement of the infarct and viable myocardium. Pearson's correlation to generate any association between stem cell engraftment/peri-infarct viability and functional restoration and/or clinical outcome.

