## **2 Study Objectives**

This is a first-in-human clinical trial of combined manganese-enhanced MRI(MEMRI) and delayed-enhanced MRI(DEMRI) to determine reliable detection and clinical significance of peri-infarct injury in both the ventricles and atria. An IND approval was obtained to utilize EVP1001-1 to assess peri-infarct injury in patients with ischemic or dilated cardiomyopathy atrial fibrillation and those who undergo stem cell therapy for these indications. In preparation for a Phase I/II clinical trial, an initial safety study of 6 patients has been completed and no adverse events were observed. This proposal will enable a clinical trial of 50 patients to evaluate the safety and efficacy of MEMRI-DEMRI to characterize peri-infarct injury.

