## 7 Statistical Plan

### 7.1 Sample Size Determination

The total number of 0 patients will power this study adequately, however as we have extended the protocol to include the atrial fibrillation participants (and extra 60 pts) the difficulty in imaging the atria, coupled with the thin atrial walls, means that we expect a difference in DEMRI volume of 40 (+ or - 20) in participants with early disease and 60 (+ or - 20) in participants with advanced disease. Accordingly, 60 participants will be needed for the additional cohort. Our published pre-clinical study in 13 swine demonstrated the infarct volume percentage difference of 9% between MEMRI and DEMRI ( $p<0.001$ ). This difference will enable significant delineation of the changes in the peri-infarct viability between the cell therapy and control arms. The preliminary porcine data presented above demonstrated a mean of 100% increase in the CNR of the peri-infarct region and a mean of 50% decrease in the scar volume, suggesting robust MEMRI signal detection of stem cell engraftment and increased peri-infarct viability. Furthermore, the clinical trial in 6 ICM patients demonstrated significant difference in the infarct volume between MEMRI defect and DEMRI enhancement. This difference between MEMRI and DEMRI represents PIR assuring reliable detection of the PIR. Employing these data, in order to detect a mean difference of 20% in MEMRI signal of stem cell engraftment and MEMRI-DEMRI signal of peri-infarct viability with a standard deviation of 5%, the t-test sample size calculation in this study has 90% power at the alpha 0.05 significance level, assuming an equal variance between the two distributions.

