### 7.3 Subject Population(s) for Analysis

We expect to enroll 60 patients with various cardiomyopathies including NICM, ICM, and ACM (dilated cardiomyopathy, ischemic cardiomyopathy, and atrial cardiomyopathy). Our goal is to demonstrate improved sensitivity and specificity of identifying viable myocardium and PIR in the ventricles and atria in various cardiac patients to help improve clinical management

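### The t-test in Section 7.2 shows whether the average MEMRI-DEMRI difference is non-zero; it cannot show whether peri-infarct injury is reliably detected in individual patients, and no other method in 7.2 does.

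*Combined protocol and SAP*

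**What the plan says.** The opening of Section 2 states that the trial is "to determine reliable detection and clinical significance of peri-infarct injury in both the ventricles and atria". Specific Aim 1, the primary objective, is to evaluate how well combined MEMRI-DEMRI characterises this injury in ventricles and atria.

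Section 7.2 lists two methods. One is "Student's t-test to compare MEMRI and DEMRI measurement of the infarct and viable myocardium"; whether it is paired is not stated. The other is a Pearson correlation with function or clinical outcome, which does not bear on detection.

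Section 7.1, after noting a significant mean difference in the six-patient pilot, concludes: "This difference between MEMRI and DEMRI represents PIR assuring reliable detection of the PIR".

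Per-patient measures appear in three other places:

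- Section 3.1 (Parameters to be Measured) bases primary efficacy on reading each heart as normal or abnormal, with infarction, ischemia or both. From this come sensitivity, specificity and related measures.
- Section 3.2 judges infarct or ischemia against echo and gadolinium MRI, and also against patient outcomes.
- Section 7.3 states a goal of better sensitivity and specificity for viable myocardium and the peri-infarct region.

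None of these has an estimator, confidence interval or target in Section 7.2. No section says what counts as a detected peri-infarct region in one patient.

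**The concern.** Reliable detection is a statement about individual patients, and Section 7.3 makes clear that the results are meant to inform patient care. A t-test, paired or not, asks whether the mean difference is zero. With 50 or more patients it can reject that hypothesis while the difference varies widely and is absent in a sizeable minority.

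Section 7.1 already moves from a mean difference to assured detection when it interprets the pilot. If the main result is read the same way, Aim 1 could appear to be met without anyone knowing in how many patients, or in which disease groups, the two scans differ.

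**Working it through.** **1. The plan's own power figure.** Section 7.1 gives a target "in order to detect a mean difference of 20% in MEMRI signal of stem cell engraftment" (and in the MEMRI-DEMRI signal of peri-infarct viability) "with a standard deviation of 5" percent, and says the design "has 90% power at the alpha 0.05 significance level, assuming an equal variance between the two distributions". Two-sided testing is assumed here.

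- Normal approximation, two groups: n = 2 × (1.960 + 1.282)² × (5/20)² = 1.3, so 2 per group.
- Noncentral t: 3 per group gives 94.8%; 3 pairs give 90.8% if 5 is the SD of the differences.
- At 25 or more per group, power is about 100%.

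The stated 90% therefore matches none of the sample sizes in the document: 50 (Study Summary, Section 2), 60 (Sections 1.4 and 7.3) and 120 (Sections 1.1, 4.3 and 8.3.1). Section 7.1 itself prints 0. At any of these sizes, significance says little about individual patients.

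**2. What a just-significant result allows.** Assume normal within-patient differences and a paired two-sided 0.05 test. The smallest significant mean, in SD units, is d = t(0.975, n−1)/√n. The share of patients with a zero or reversed observed difference is Φ(−d).

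| n | t | d | Φ(−d) |
|---|---|---|---|
| 50 | 2.010 | 0.284 | 38.8% |
| 60 | 2.001 | 0.258 | 39.8% |
| 120 | 1.980 | 0.181 | 42.8% |

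If the test is unpaired, d = t(0.975, 2n−2) × √(2/n) / √(2(1−r)), where r is the within-patient correlation (not given). At n = 50 the share is 38.9%, 34.6% or 26.5% for r = 0, 0.5 or 0.8.

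**3. The same share at the effects the plan expects.**

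- Plan's effect, 5 as the SD of the differences: d = 20/5 = 4, share about 0.003%; 95% range 20 ± 1.96 × 5 = 10.2 to 29.8.
- Plan's effect, 5 as the SD of each measurement with r = 0: d = 20/(5√2) = 2.83, share about 0.2%.
- Pilot (Sections 1.1 and 1.4: 39±11% against 16±3%, difference 23 points; SD of the difference not given): SD = √(121 + 9 − 2r × 33), which is 11.4 at r = 0 and 8.4 at r = 0.9. The share is 2.2% and 0.3%; the 95% range is 0.7 to 45.3 and 6.5 to 39.5.

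**4. A large t-statistic does not settle it either.** As an assumed scenario, let 40% of patients have a true difference of zero and 60% a true difference of 20, with SD 5 around each. Then the mean is 0.6 × 20 = 12, the variance is 25 + 0.4 × 0.6 × 400 = 121, and the SD is 11. At n = 50 the expected t is about 12/(11/√50) = 7.7, a very small p-value. The 95% range, 12 ± 1.96 × 11 = −9.6 to 33.6, includes zero and would reveal the problem.

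**The case against.** The strongest reply is that patient-level evaluation is already planned in Sections 3.1, 3.2 and 7.3. This stands to a point: a reader might infer that the t-test is the only comparison of the two scans anywhere in the plan, and that is not so. But none of these measures reaches Section 7.2, and those in 3.1 and 3.2 address infarction and ischemia. Section 3.2 also uses gadolinium MRI as part of its reference. Sections 1.3 and 1.4 locate the peri-infarct region where the two scans disagree, so scoring MEMRI against gadolinium would count that disagreement as MEMRI error.

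Second, the Section 7.1 sentence interprets the pilot; it is not a decision rule, and Aim 1 says characterise. That is correct. Nothing in the plan commits the sponsor to reporting a p-value as reliable detection. The gap is that nothing else is planned that could support that claim.

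Third, the pilot difference was large, with DEMRI higher in all six patients. Even if each of the six showed it individually, the exact two-sided 95% upper bound for the share who do not is 1 − 0.025^(1/6) = 46%. The pilot patients had ischemic disease and a mean LVEF of 32%. Section 4.1 now admits dilated cardiomyopathy, EF up to 50 and atrial fibrillation.

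Fourth, the two methods are expected to differ, so limits of agreement are not a measure of reliability. This also stands: the range mixes true variation in peri-infarct size with measurement error, and should be reported as such. It describes the net volume difference. If the peri-infarct region is instead defined as the overlap of the two signals, it cannot be negative and the signed range does not apply to it.

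**Conclusion.** The concern holds in this limited form: Section 7.2 offers only a test of the mean for a question about individual patients, and the per-patient measures named elsewhere are not carried into it.

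The shares of 39%, 40% and 43% illustrate what a just-significant paired result allows under normality. A reader might take them to mean that about four in ten patients will show no difference. The documents do not support that: the plan's own effect and the pilot both imply about 2% or less, and the shares count reversed as well as zero observed differences.

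Nor can it be said that the share will be larger in non-ischemic or atrial fibrillation patients. It may be, but no MEMRI-DEMRI difference is given for them; the atrial figures in Section 7.1 (40 and 60, each ±20) compare DEMRI volume between early and advanced disease.

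Sidedness, pairing and within-patient correlation are not stated and are assumptions here. The change should be made, but the point does not invalidate the design.

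**What to change.** In Section 7.2:

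- Analyse within-patient (paired) differences, DEMRI volume minus MEMRI defect volume.
- Report by chamber and by disease group (ICM, NICM, AF): the mean difference with 95% CI; the 95% range of individual differences (mean ± 1.96 SD) with a Bland-Altman plot; and the proportion of patients with DEMRI volume greater than MEMRI defect volume, with an exact 95% CI.
- State that a significant mean difference alone will not be reported as reliable detection, and that the range reflects both true variation in peri-infarct size and measurement error.

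The proportion should be read with the range, since it is not itself a detection rate: in the step 4 scenario only about 20% of patients (half of the 40%) would have a zero or reversed observed difference.

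A masked same-reader repeat read to estimate measurement error is optional and should not be the sole criterion. If done, state that the SD is per exam and report its interval; with 10 repeat pairs that interval runs from about 0.7 to 1.75 times the estimate.

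The cost is wording and a little more analysis, with no new scans or patients. The headline will be less favourable if the range includes zero. Subgroup estimates will be imprecise: if 50 patients split evenly (an assumption), a group of about 17 with all differences positive would still have a lower bound of 0.025^(1/17) = 80%.

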## 1.1 Background

- This is a first-in-human clinical translation of manganese-enhanced MRI(MEMRI) to assess the peri-infarct injury in patients with patients with ischemic or dilated cardiomyopathy with an EF less than or equal to 50 or patients with paroxysmal or persistent atrial fibrillation
- and those who received stem cell therapy for these indications. The PI recently obtained an approval for an Investigational New Drug (IND # [REDACTED]) to conduct a clinical trial of MEMRI contrast agent (EVP1001-1, Eagle Vision, Downingtown, PA). Funding of this proposal will enable a clinical trial of 120 patients with ischemic or dilated cardiomyopathy with an EF less than or equal to 50 or patients with paroxysmal or persistent atrial fibrillation to evaluate the safety and efficacy of sequential acquisition of MEMRI and delayed-enhanced MRI (DEMRI) for precise tissue characterization of the peri-infarct region (PIR). This novel technique designed to integrate the biology of the viable cardiomyocytes with the anatomy of the scar will predict future cardiovascular events (CVE), in this highly morbid patient population. ICM and NICM are the primary etiology of advanced heart failure (HF) while ACM is a frequent sequela of HF. Today, HF is the leading diagnosis of hospital admission in the US. Our studies have confirmed a direct association between the presence of PIR and the occurrence of atrial and ventricular arrhythmia and remodeling, resulting in high morbidity and mortality in advanced HF. PIR has been recognized as an important substrate to trigger atrial and ventricular arrhythmias and stem cells may provide an alternative therapy for PIR. Studies employing DEMRI has identified atrial scar as the potential cause of atrial arrhythmia. This proposal contains novel hypotheses well-grounded on the following 2 innovations: (1) MEMRI for management of HF. An alternative approach is to employ manganese (Mn2+), which targets the viable myocardium. Mn2+ is specific to the L-type calcium channels and complements the non-viable scar delineated by DEMRI. The dual MEMRI-DEMRI approach will, therefore, identify the viable and, potentially, salvageable cardiomyocytes outside the core infarct zone but inside the PIR. Our recently published study demonstrated that an overlap of DEMRI and MEMRI signal denoted a significant number of live cardiomyocytes (MEMRI-positive) within the non-viable (DEMRI-positive) region. This innovation will profoundly impact the clinical management of the advanced HF patients and AA patients including atrial fibrillation. EVP1001-1 allows highly effective intracellular targeting of viable cardiomyocytes with high level of safety and unique magnetic properties. (2) Assessment of therapeutic response using MEMRI. EVP1001-1 is rapidly transported, intra-cellularly, to mitochondria rich tissue such as heart, liver, and kidney, demonstrating significant enhancement indicative of cell metabolism and viability. High dose clinical safety studies of SeeMoreTM with safety index of 45-90 correspond more favorably than the widely used clinical imaging agents (10-20 for iodinated X-ray products and 20-60 for gadolinium). This specific, non-perfusion dependent distribution due to active intracellular uptake is one of the key attributes that offers real-time assessment of therapeutic response, using cardiac cellular imaging. A clinical safety trial in 6 patients have demonstrated negligible uptake in the intra-infarct region (IIR), reduced uptake in the PIR, and significantly higher uptake in the normal tissue to generate positive signal. In this trial, the mean LVEF was 32±4%. The DEMRI vs. MEMRI (scar/myocardial volume) demonstrated significantly higher measurement of the scar by DEMRI in all patients (39±11%\* vs. 16±3%, \*p<0.01) These data indicate 2 important findings: 1) significant over-estimation of the scar by DEMRI and 2) quantitative difference of the scar volume between MEMRI and DEMRI delineates the PIR. This precise characterization allows accurate assessment of the efficacy of novel therapeutic agents in restoring the PIR at both cellular and tissue levels. EVP1001-1 is a new manganese (Mn)-based intravenous imaging agent being developed to enhance magnetic resonance imaging (MRI). While Mn has long been known to have desirable magnetic and kinetic properties for MRI, use in humans was not initially possible due to cardiovascular depression and electrocardiogram (ECG) changes, including prolongation of PR and QTc intervals, associated with intravenous administration. Chelation of Mn, as had been done with gadolinium for use with MRI, provided relevant safety, but sacrificed desirable magnetic and kinetic properties. EVP1001-1 provides Mn in a form that maintains the desired magnetic and kinetic properties while overcoming the cardiovascular toxicity of Mn. EVP1001 is taken up into heart cells (primarily via addition of calcium to avoid cardiotoxic effects; please refer to patent listed below). The potential to distinguish healthy heart tissue from unhealthy heart tissue based on a specific sustained pattern of enhancement provides a basis for evaluating the performance of EVP1001-1 in heart patients. MRI offers benefits over other imaging technologies. Relative to radioactive nuclear imaging procedures, MRI is 3- dimensional, provides good soft tissue discrimination, and is of high spatial and temporal resolution. These features have been reported to identify smaller defects (e.g., subendocardial infarcts) and match angiographic results more closely than other modalities such as SPECT. It may be possible to enhance the utility of MRI for heart disease further through the use of an imaging agent that is specifically taken up into heart cells. EVP1001-1 is the only cardiac-specific agent being developed for this purpose. Unlike nuclear perfusion agents, EVP1001-1 is not radioactive and does not require special handling, shielding, transport or storage. In addition, the specific pattern of enhancement achieved in the heart muscle persists

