In both sub-acute and chronic porcine ischemia-reperfusion injury (IR) models, MEMRI demonstrated a consistent anteroseptal infarct pattern from the mid-LAD IR injury). MEMRI of the hAMSC group revealed discrete foci of high contrast-to-noise ratio (CNR) *within* infarct and peri-infarct zones, which were absent in control group. These hyperintense foci increased in CNR over the 3-week and 6-week time course after cell delivery in comparison to the control group. To confirm the specificity of the positive MEMRI signal for hAMSC engraftment, the hAMSCs for one sub-acute and one chronic IR swine were modified with injection of ~20% herpes simplex virus-thymidine kinase (HSV-tk) PET reporter gene (PET-RG) transduced hAMSCs. Serial cardiac PET-CT scans (day 0, day 7, and day 21 or 38 after injection) were then performed using a specific 9-[ $\text{F}$ ]fluoro-3-(hydroxymethyl) butyl] guanine (F-FHBG) radioisotope, which are phosphorylated and retained only by the viable cells expressing PET-RG. At each time point, apical PET signal co-localized with the site of cell injection and MEMRI signal. Quantitative assessment of PET activity from these regions indicated significantly higher radiotracer uptake compared to surrounding myocardium by approximately 25-fold. When plotted according to the AHA 16-segment model, the integrated MEMRI and PET signal within each segment showed a significant linear correlation in both the sub-acute and chronic IR models. The increased MEMRI CNR tracked the survival of hAMSCs longitudinally, suggesting that the hAMSCs engrafted *in vivo* up to 6 weeks.

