#### **4.3 Subject Recruitment and Screening**

This is an open-label, baseline-controlled study to be conducted. Adult male or non-pregnant female patients who have been referred for evaluation of cardiomyopathy and atrial fibrillation and patients who have received stem cell therapy related to these indications will be recruited. An initial cohort study of 6 patients to conduct safety evaluation was conducted before proceeding with 120 additional patients. In the initial cohort, a patient was dosed based on the Phase 1 and 2 clinical trial data evaluation completed by Eagle Vision Pharmaceutical, Inc. Subjects were excluded if they had received an investigational device within 30 days prior to administration of EVP1001-1; had a history of drug abuse or alcoholism; were taking a digitalis preparation; had a history of torsades; had NYHA Grade IV heart failure; had abnormal liver function tests or a history of liver disease; had uncontrolled hypertension; had abnormal calcium, potassium or hemoglobin values at baseline; if they develop a cardiac arrhythmia prior to or during either of the exercise tests-- EVP1001-1 was not administered. The same parameters will apply to the new group of subjects.

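### Sections 7.1 and 7.2 treat stem cell engraftment as a measured variable, but the described procedures give no measure of it distinct from native peri-infarct viability

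*Combined protocol and SAP*

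**What the plan says.** Section 7.2 specifies "Pearson's correlation to generate any association between stem cell engraftment/peri-infarct viability and functional restoration and/or clinical outcome". It does not define engraftment or say how it is obtained from the images. Section 7.1 sizes the study "in order to detect a mean difference of 20% in MEMRI signal of stem cell engraftment" and, in the same sentence, in a MEMRI-DEMRI signal of peri-infarct viability, with SD 5%, 90% power and alpha 0.05.

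Other sections interpret MEMRI signal in or around scar in two ways:

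- **Native viability.** Section 1.1 reports that "an overlap of DEMRI and MEMRI signal denoted a significant number of live cardiomyocytes (MEMRI-positive) within the non-viable (DEMRI-positive) region". Section 7.1 turns this into a volume: "This difference between MEMRI and DEMRI represents PIR assuring reliable detection of the PIR".
- **Engraftment.** Section 1.3 describes bright MEMRI foci in the infarct and peri-infarct zones of cell-treated swine. PET reporter-gene imaging was added "To confirm the specificity of the positive MEMRI signal for hAMSC engraftment".
- **Both.** Section 7.1 describes one set of porcine changes (CNR up by a mean of 100%, scar volume down by a mean of 50%) as "suggesting robust MEMRI signal detection of stem cell engraftment and increased peri-infarct viability".

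On enrolment, section 4.3 says that "patients who have received stem cell therapy related to these indications will be recruited". Section 1.1 also speaks of patients already treated, whereas section 2 and section 1.4 speak of patients who undergo, or are undergoing, cell therapy. Sections 7.2 and 7.3 do not say how recipients are to be handled.

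**The concern.** A correlation needs a variable that is defined and measured in each patient. Engraftment does not exist in patients who never received cells. In those who did, the plan gives no way to tell manganese uptake by graft from uptake by surviving native myocardium. Followed literally, section 7.2 could report that engraftment is associated with function or outcome when the measured quantity is viable tissue of either origin.

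The second issue touches the primary objective. If PIR is the difference between the DEMRI and MEMRI volumes, graft uptake inside the scar shrinks the MEMRI defect and enlarges apparent PIR. In recipients, part of what is called salvageable native tissue could be transplanted cells, and nothing in the analysis plan would show it.

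**Working it through.** **1. The plan's own figure.** Difference 20, SD 5, power 90%, alpha 0.05 (section 7.1). By the two-sided normal approximation, n per group = 2(1.960 + 1.282)² / (20/5)² = 2 × 10.51 / 16 = 1.31, so 2. The exact t-test needs 3 per group (power 0.948), or 3 pairs if paired (0.909). With 50, 60 or 120 patients split equally, power is about 100%. The stated 90% is not reproduced at any total in the document, and the total in 7.1 reads 0 in the text available. That is a separate defect, and this point does not depend on it.

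**2. What supported the engraftment reading in swine, and what this trial has.**

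| Element | Swine (section 1.3) | This trial |
|---|---|---|
| Comparison without cells | Control group; foci absent there | Non-recipients can be enrolled, but 7.2 sets no comparison |
| Repeat imaging | CNR of foci followed at 3 and 6 weeks | One MEMRI-then-DEMRI session in 3.1; section 6 only refers back to section 3 |
| Independent label | PET reporter gene in one sub-acute and one chronic animal | None described |
| Reading rule | Discrete foci of high CNR | None; 3.1 and 3.3 list location, size, conspicuity and confidence of disease |

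No scan before cell therapy is described either.

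**3. What one correlation can show in recipients.** Suppose that, with no reading rule, the measured signal is S = N + G, with native part N and graft part G independent, and g = var(G)/var(S). Then

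corr(S, Y) = √(1 − g) · r_N + √g · r_G,

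where r_N and r_G are the correlations of each part with outcome Y. The documents give none of these values; those below are assumptions.

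| g | Native only (r_N = 0.5, r_G = 0) | Graft only (r_N = 0, r_G = 0.5) |
|---|---|---|
| 0.25 | 0.433 | 0.250 |
| 0.50 | 0.354 | 0.354 |
| 0.75 | 0.250 | 0.433 |

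At g = 0.50 the two explanations give the same coefficient. An observed 0.433 or 0.250 fits either one, depending on an unknown g. The coefficient cannot be assigned to engraftment.

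**4. Effect on PIR.** Let f be the share of recipients and b the graft-related volume, in points of myocardial volume, that fills the MEMRI defect in a recipient, with the DEMRI volume unchanged. The pooled PIR mean then rises by f × b. For scale, the pilot difference (sections 1.1 and 1.4) is 39 − 16 = 23 points. Both f and b are assumed:

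- f = 0: no effect.
- f = 10%, b = 5: 0.5 points (0.5/23 = 2%).
- f = 25%, b = 9: 2.25 points (10%).
- f = 50%, b = 11.5: 5.75 points (25%).

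These lines show how the effect scales. They do not estimate it.

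**5. Could graft be present at the scan?** The swine evidence runs to 6 weeks (42 days). Section 4.2 excludes an investigational drug or device within the previous 30 days. If the cell product counts as one, days 31 to 42 remain open. No maximum interval is stated, so later scans fall outside the period that the swine data cover.

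**The case against.** The strongest reply is that the plan does not treat the two constructs as identical. Section 7.1 pairs engraftment with MEMRI signal and viability with a MEMRI-DEMRI signal. Section 1.3 describes different appearances: native peri-infarct tissue had lower MEMRI SNR than remote myocardium, while cells appeared as discrete bright foci. A reader might infer from the shared signal that graft and native tissue are inseparable in every recipient, and the documents do not support that. A rule based on appearance is conceivable. What stands is that no threshold, reader instruction or human validation is given, and 7.2 joins the two with a slash.

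Other strong readings also fail:

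- **Only one scan is possible.** Section 3.1 describes one session but sets no limit. The synopsis gives times per exam and three days per patient, and the procedures flowchart listed in section 14 is not in the text available.
- **There is nobody to compare with.** Section 5.3 says only that assignment to treatment groups does not apply. Non-recipients can be enrolled.
- **The porcine halving of scar sizes the bias.** Section 7.1 does not say which technique measured it. Halving the MEMRI defect alone would widen the pilot difference; halving both volumes gives 19.5 − 8 = 11.5 points, below 23. Part of the porcine change is also attributed to real viability, which PIR should count.

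It is also fair that the numbered aims, the endpoints, section 7.3 and the synopsis's correlation line do not mention engraftment. The term may be carried over from the wider proposal in section 1.4. It still stands in 7.1 and 7.2, which govern the analysis.

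**Conclusion.** The concern holds for the plan as written. Engraftment is named in the power statement and as a correlate, yet the described procedures contain no engraftment-specific measure, and the supports used in swine are absent. This conclusion does not depend on how many recipients enrol.

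The effect on PIR is conditional. It needs recipients in the sample and surviving graft that takes up manganese. Graft uptake within unchanged DEMRI scar would raise apparent PIR. Its size cannot be derived, because recipient numbers, time since therapy and graft share are all unstated, and prior cell therapy is not among the inclusion criteria in section 4.1. Correlations of peri-infarct viability in patients without cell therapy are unaffected by this point.

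**What to change.** - Remove stem cell engraftment from 7.1 and 7.2. Name the correlate peri-infarct viability and define it from the MEMRI-DEMRI comparison.
- Record prior cell therapy (yes/no, with date) in the medical history that section 3.1 already requires.
- Report the PIR result and its correlations by cell-therapy status, including an analysis that excludes recipients, and make no engraftment claim. Recipients are enrolled deliberately, so they need not be dropped from the study.
- Reconcile sections 1.1 and 4.3 (therapy already received) with sections 2 and 1.4 (therapy being undergone).

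The cost is protocol wording, one history item, slightly more analysis and less precision in the analysis without recipients. Correlations in a small subgroup will be weak evidence. By Fisher's z, with standard error 1/√(n − 3), an assumed r of 0.4 has a 95% interval of −0.31 to 0.82 with 10 patients and 0.01 to 0.69 with 25. A small recipient group should therefore be reported descriptively.
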